**Confidential Information**

**No use or disclosure outside AbbVie is permitted without prior written authorization from AbbVie.**

## 1.1 Protocol Amendment: Summary of Changes

### Previous Protocol Versions

Protocol	Date
Original	12 March 2014
Amendment 1	02 July 2015

The purpose of this amendment is to incorporate the changes summarized below.

- **Applied administrative changes throughout protocol.**

*Rationale for change: Text was revised to improve consistency and readability, and/or provide clarification.*

- **Number of Subjects to be Enrolled and number of Study Sites** were changed throughout the protocol.

*Rationale for change: Due to low recruitment rate, the study population sample size was reviewed from approximately 200 to approximately 50, and number of study sites clarified to approximately 25. Changed to reflect to the current standard protocol template and to be consistent throughout protocol.*

- **Section 1.2, Synopsis.** Updated

*Rationale for change: Synopsis was revised to be consistent with Amendment 2 revisions.*

- **Section 5.2.1, Inclusion Criteria: Criteria 5** updated.

*Rationale for change: Criteria updated as per AbbVie latest protocol standard text and add precision to the inclusion of female of childbearing potential and male subject with childbearing potential female partner.*

- **Section 5.2.2, Exclusion Criteria: Criteria 17** added.

*Rationale for change: Criteria added as per AbbVie latest protocol standard text and to clarify exclusion in regards to male subject considering fathering a child or donating sperm*

- **Section 5.2.4, Contraception Recommendations and Pregnancy Testing:** new

*Rationale for change: Section added as per AbbVie latest protocol standard text and to add precision to acceptable contraception.*

- **Section 5.3.1.1, Study Procedures: Hepatitis B and Hepatitis C Testing.**  
*Rationale for change: Text updated to clarify exclusion of subjects with a positive HBc Ab Total test, indicating a previous Hep B exposure, link to a risk of reactivation or worsening of hepatitis B with MTX.*
- **Section 5.3.1.1, Study Procedures: Pregnancy Tests.**  
*Rationale for change: Addition of pregnancy tests at week 8 and 16 due to methotrexate embryotoxicity, and teratogenic effects and AbbVie latest protocol standard text.*
- **Section 8.2, Determination of Sample Size.** Updated.  
*Rationale for change: Section revised to reflect modification of study sample size .*

## 1.2 Synopsis

AbbVie Corporation	Protocol Number: W14-406
Name of Study Drugs: Adalimumab and Methotrexate	Phase of Development: 3b
Name of Active Ingredients: Adalimumab and Methotrexate	Date of Protocol Synopsis: 22/Apr/2016
Protocol Title: Concomitant longitudinal evaluation of adalimumab with methotrexate in the real world: the CLEAR study	
Objective(s):  Primary objective:  To determine the proportion of primary and secondary sub-optimal responders to adalimumab (ADA) monotherapy  (sub-optimal responders defined as subjects with an unsatisfactory response to psoriasis (Ps) treatment based on Investigator assessment)  with a PGA $\geq 3$ , and a PASI $\geq 5.0$ who have a satisfactory response after 16 weeks of treatment with ADA/methotrexate (MTX) combination therapy, based on Investigator and subject satisfaction assessments (using satisfaction questionnaires).  Secondary objectives:  
 
• To determine the proportion of primary and secondary sub-optimal responders to ADA monotherapy (sub-optimal responders defined as subjects with an unsatisfactory response to treatment based on Investigator assessment) with a PGA <math>\geq 3</math> and a PASI <math>\geq 5.0</math> who reach PASI 50, PASI 75 and PASI 90 16 weeks after initiation of ADA/MTX combination therapy;
 
• To define the demographic and clinical profile of subjects benefiting from ADA/MTX combination therapy;
 
• To determine the magnitude, timing and maintenance of the benefit of adding MTX to ADA by assessing Investigator/subject satisfaction with treatment, PGA, PASI and Dermatology Life Quality Index (DLQI) at 8, 16 and 24 weeks after addition of MTX to therapy;
 
• To determine change in DLQI from baseline in subjects initiated on ADA/MTX treatment;
 
• To determine change in serum levels of ADA following addition of MTX and to characterize a possible correlation with changes in Investigator/subject satisfaction with treatment, PGA, PASI and DLQI over the study period. Serum levels will be evaluated at baseline (initiation of ADA+MTX) and at weeks 8, 16 and 24.
 
	
Investigator(s): Multicenter	

 Note that subjects may also be receiving topical treatments if they were prescribed prior to enrolment in the study

 Investigator assessment based on a questionnaire response; see Satisfaction questionnaire section

Study Site(s): Approximately 25 Canadian sites
Study Population: Adult subjects 18 years of age or older, with a clinical diagnosis of moderate to severe Ps for at least 6 months who have been receiving ADA monotherapy at a dose of 40 mg every-other-week (eow) or greater for at least 16 weeks and who, in the opinion of the treating Investigator, have a sub-optimal response to treatment, or have not maintained an initial positive response (secondary sub-optimal responders) (sub-optimal response and secondary sub-optimal responders defined as subjects with an unsatisfactory response to treatment based on Investigator assessment) AND have a PGA score of $\geq 3$ (or at least moderate disease) and a PASI of $\geq 5.0$ .
Number of Subjects to be Enrolled: Approximately 50
Methodology: The study entails a 24-week treatment period and a 70-day safety follow-up period. Subjects, who in the opinion of the Investigator are not responding optimally to ADA monotherapy (40 mg eow or greater) at least 16 weeks after initiating treatment (primary sub-optimal responders) or who, after an initial positive response to ADA monotherapy (40 mg eow or greater) have failed to maintain an optimal level of response (secondary sub-optimal responders) (sub-optimal responders defined as subjects with an unsatisfactory response to treatment based on Investigator assessment) and have a PGA $\geq 3$ and a PASI $\geq 5$ will be potentially eligible for participation in the study. Potential subjects receiving ADA 40 mg once weekly will only be eligible for the study after a wash-out period of 8 weeks on ADA 40 mg eow. Following identification of potential subjects, the Investigator will arrange a pre-screening visit to discuss treatment status with the subject and outline the proposed study with the understanding that the subject must meet all inclusion criteria before participation. If subjects provide written consent, they will then complete a satisfaction questionnaire, and PGA and PASI status will be determined at a screening visit and inclusion/exclusion criteria assessed. Subjects eligible for participation in the study must have a PGA score of $\geq 3$ and a PASI of $\geq 5$ .
Data collected at a baseline visit will include: subject demographics, disease history, comorbidities, vital signs, laboratory investigations, PGA, PASI and DLQI scores and serum levels of ADA. Subjects will continue to self-administer ADA (40 mg eow) but will have oral MTX added to their treatment at a dose to be defined by the Investigator. At site visits 8, 16 and 24 weeks after initiation of ADA/MTX, the following parameters will be assessed: physician assessment of disease status (using a satisfaction questionnaire); subject self-assessment of disease status (using a satisfaction questionnaire); PGA; PASI; DLQI; adverse events (AEs); serum levels of ADA.
Satisfaction questionnaire: Both Investigators and subjects will be asked how satisfied they are with the Ps control provided by the subject's current treatment. The provided responses will be: completely dissatisfied; moderately dissatisfied; slightly satisfied; highly satisfied; completely satisfied. Subjects with an Investigator assessment of completely or moderately dissatisfied with treatment will be categorized as a sub-optimal responder.
The 70-day safety follow-up period begins from the last dose of ADA. Subjects will be discontinued from the study if they withdraw consent or if they are deemed unsuitable to continue for any reason by the Investigator in consultation with the AbbVie Medical Monitor.

**Diagnosis and Main Criteria for Inclusion/Exclusion:****Main Inclusion:**

1. Subjects who have been on ADA monotherapy (40 mg eow or greater) for at least 16 weeks but who in the opinion of the Investigator have shown a sub-optimal response to treatment and have a PGA of  $\geq 3$  and a PASI of  $\geq 5$ ; or  
Subjects who after an initial positive response to ADA monotherapy (40 mg eow or greater) have failed to maintain an optimal level of response, based on the opinion of the Investigator, and have a PGA of  $\geq 3$  and a PASI of  $\geq 5$ ;
2. Subjects who are receiving 40 mg ADA once weekly must be on ADA 40 mg eow for 8 weeks prior to screening;
3. Subjects with at least a 6 month history of chronic plaque Ps;
4. Subjects greater than or equal to 18 years of age;
5. If female, subject is either not of childbearing potential, defined as postmenopausal for at least 1 year or surgically sterile or is of childbearing potential and is practicing birth control;
6. The results of the serum pregnancy test performed during the Screening Period and urine pregnancy test performed at the Baseline Visit must be negative;
7. Subject is judged to be in good general health as determined by the Principal Investigator;
8. Subjects must be evaluated for latent TB infection;
9. Subjects must be able and willing to provide written informed consent and comply with the requirements of the study protocol;
10. Subjects must be willing and able to self-administer subcutaneous (SC) injections or have a qualified person available to administer SC injections.

**Main Exclusion:**

1. Subject has any contraindications to MTX or ADA;
2. Subject has a previous failed response or poor tolerance to ADA;
3. Subject has a poorly controlled medical condition which, in the opinion of the Investigator, would put the subject at risk by participation in the study;
4. Subject has a history of clinically significant hematologic, renal or liver disease;
5. Subject has a history of neurologic symptoms suggestive of central nervous system (CNS) demyelinating disease and/or diagnosis of central demyelinating disease;
6. Subject has evidence of dysplasia or history of malignancy (including lymphoma and leukemia) other than a successfully treated non-metastatic cutaneous squamous cell or basal cell carcinoma or localized carcinoma in situ of the cervix;
7. Subject has a history of listeriosis, histoplasmosis, untreated TB, persistent chronic infections, or recent active infections requiring hospitalization or treatment with intravenous (iv) anti-infectives within 30 days or oral anti-infectives within 14 days prior to the Baseline visit;
8. Subject is known to have immune deficiency, history of HIV or is immunocompromised;
9. Subject currently uses or plans to use anti-retroviral therapy at any time during the study;
10. Female subject who is pregnant or breast-feeding or considering becoming pregnant during the study or for 150 days after the last dose of study medication;

**Main Exclusion (contd.):**

11. Subject has a history of clinically significant drug or alcohol usage in the last year or cannot maintain an alcohol intake of 30 g a day or less throughout the study (one standard drink is defined as 180 mL/6 oz (approx. 10 g) of wine, 360 mL/12 oz (approx. 15 g) of regular beer, or 45 mL/1.5 oz (approx. 10 g) of spirits;
12. Screening clinical laboratory analyses show any of the following abnormal laboratory results:
  - Aspartate transaminase (AST) or alanine transaminase (ALT) > 2x the upper limit of normal (ULN);
  - Serum total bilirubin > 1.5 mg/dL (> 26 micromol/L), except for subjects with Gilbert's Syndrome;
  - Creatinine > 1.5 mg/dL (133 micromol/L) in subjects ≤ 65 years old and > upper limit of normal range in subjects > 65;
  - Positive Hepatitis B or C serology indicative of previous or current infection.
13. Subject is considered by the Investigator, for any reason, to be an unsuitable candidate for the study;
14. The following treatments are prohibited for all subjects during the study:
  1. Phototherapy (PUVA (within 4 weeks of the Baseline Visit) and/or UVB (within 2 weeks of the Baseline Visit);
  2. Other biologic therapies (including any other anti-TNF) within 4 weeks of the Baseline Visit;
  3. Any investigational agents of chemical or biologic nature within a minimum of 30 days or 5 half-lives (whichever is longer) of the drug prior to the Baseline visit ;
  4. Any other systemic drug therapies for Ps within 4 weeks of the Baseline Visit;
  5. Oral or injectable corticosteroids, new prescription topical therapies, or changes in the concentration of current prescription topical therapies (including corticosteroids) that are being used, within 2 weeks of the Baseline Visit. Subjects may continue using previously prescribed topical therapies (including corticosteroids) during the study.
15. Prior exposure to biologics that have a potential or known association with Progressive multifocal leukoencephalopathy PML (i.e., natalizumab (Tysabri®) or rituximab (Rituxan®));
16. Subjects with any active viral infection that based on the investigator's clinical assessment makes the subject an unsuitable candidate for the study;

**Investigational Product(s):** ADA and MTX**Dose(s):**

ADA: 40 mg eow beginning at study Week 0 through Week 22.

MTX: Dose is up to the discretion of the investigator but recommended dose should be between 10 and 25 mg/week, beginning at Week 0 through Week 23. The minimum initial dose of MTX should be 10 mg/week. MTX dose can be increased at any time over the study period, based on the clinical judgment of the Investigator.

**Mode of Administration:**

ADA: SC injections self-administered by subjects via pens.

MTX: Oral administration.

**Reference Therapy:**

There is no reference therapy in this study

**Dose(s):****Mode of Administration:**

**Duration of Treatment:** ADA will be administered for 24 weeks (last dose of ADA will be at Week 22); following this period decision to continue ADA will be at the discretion of the Investigator; Study-related MTX will be administered for 24 weeks (last dose of MTX will be at Week 23); following this period decision to continue MTX will be at the discretion of the Investigator.

**Criteria for Evaluation:**

**Efficacy:** The primary efficacy endpoints will be:

- Based on investigator assessment, the proportion of subjects (primary and secondary sub-optimal responders) achieving a satisfactory response to ADA + MTX treatment after 16 weeks (satisfactory response defined as highly or completely satisfied with subject's therapy using the satisfaction questionnaire);
- Based on subject self-assessment, the proportion of subjects (primary and secondary sub-optimal responders) achieving a satisfactory response to ADA + MTX treatment after 16 weeks (satisfactory response defined as highly or completely satisfied with therapy using the satisfaction questionnaire).

Secondary efficacy endpoints will include:

- The proportion of subjects (primary and secondary sub-optimal responders) achieving 50%, 75%, 90% and 100% reductions in PASI at 8, 16 and 24 weeks after initiation of ADA + MTX (change in PASI based on score at initiation of ADA + MTX therapy);
- The proportion of primary sub-optimal responders achieving 50%, 75%, 90% and 100% reductions in PASI at 8, 16 and 24 weeks after initiation of ADA + MTX (change in PASI based on score at initiation of ADA + MTX therapy);
- The proportion of secondary sub-optimal responders achieving 50%, 75%, 90% and 100% reductions in PASI at 8, 16 and 24 weeks after initiation of ADA + MTX (change in PASI based on score at initiation of ADA + MTX therapy);
- The proportion of subjects on ADA 40 mg eow prior to baseline or 40 mg once weekly prior to wash-out achieving 50%, 75%, 90% and 100% reductions in PASI 16 weeks after initiation of ADA + MTX (change in PASI based on score at initiation of ADA + MTX therapy);
- Proportion of primary and secondary sub-optimal responders achieving a clinical response defined as a PGA of "Clear" or "Minimal" at 8, 16 and 24 weeks after initiation of ADA + MTX;
- DLQI scores at baseline (at initiation of ADA + MTX) and at weeks 8, 16 and 24;
- Change and percent change in DLQI from baseline to weeks 8, 16 and 24;
- Proportion of subjects with each of the five categories of satisfaction with treatment at baseline (at initiation of ADA + MTX) and at weeks 8, 16 and 24 (subject self-assessment and investigator assessment using the satisfaction questionnaires);
- Proportion of primary and secondary sub-optimal responders achieving a DLQI score of 0 or 1, at 8, 16 and 24 weeks after initiation of ADA + MTX;
- Serum levels of ADA in subjects at baseline (at initiation of ADA + MTX) and at weeks 8, 16 and 24.

**Safety:**

Safety analyses will be performed on all subjects who receive at least one dose of ADA + MTX. Incidence of AEs, changes in vital signs, physical examination results, and clinical laboratory tests will be assessed.

**Statistical Methods:****Efficacy:**

The primary analyses will be the proportion of subjects with Ps who have a satisfactory response to ADA + MTX treatment, based on a self-assessment by subjects and an assessment by the treating Investigator. Secondary analyses will include an evaluation of the efficacy of ADA + MTX in subjects with Ps and characterization of the possible relationship between serum levels of ADA and efficacy outcomes.

This study will have a 12 month recruitment period where it is anticipated that approximately 50 subjects will be recruited. With this sample size the proportion of responders, after 16 weeks of ADA + MTX therapy, based on an Investigator assessment and subject self-assessment, can be estimated within  $\pm 4.9\%$  with 95% confidence when the point estimate is 15%, within  $\pm 6.4\%$  with 95% confidence when the point estimate is 30%, or within  $\pm 6.9\%$  with 95% confidence when the point estimate is 50%.

Due to the recent enrollment plan change, this study will only enroll 50 patients or as the number of enrollment by 31-Dec-2016. With 50 subjects the same proportion of responders can be estimated within  $\pm 9.9\%$  with 95% confidence when the point estimate is 15%, within  $\pm 12.7\%$  with 95% confidence when the point estimate is 30%, or within  $\pm 13.9\%$  with 95% confidence when the point estimate is 50%.

The primary and secondary efficacy analyses will be conducted on the ITT population (subjects who receive at least one dose of ADA and MTX). The primary efficacy analyses will also be conducted for the following subgroups:

- Subjects defined as primary sub-optimal responders at baseline, based on Investigator assessment;
- Subjects defined as secondary sub-optimal responders at baseline, based on Investigator assessment.

For the primary and secondary efficacy analyses, sub-optimal responder imputation (imputing missing satisfaction data as “dissatisfied”) will be used. In the event that greater than 5% of the satisfaction data are missing, last observation carried forward will also be carried out to impute the missing data in sensitivity analyses. Secondary outcomes will be analyzed using available data at each assessment point and changes over time will be estimated using a Mixed Model. Exploratory analysis to determine associations between ADA serum levels and PASI, PGA and DLQI scores will be carried out.

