**8.2 Determination of Sample Size**

This study should have a 30 month recruitment period where it is anticipated that approximately 200 subjects will be recruited. With this sample size the proportion of responders, defined as the proportion of subjects with a highly or completely satisfied response after 16 weeks of ADA + MTX therapy, based on an Investigator assessment and subject self-assessment, can be estimated within  $\pm 4.9\%$  with 95% confidence when the point estimate is 15%, within  $\pm 6.4\%$  with 95% confidence when the point estimate is 30%, or within  $\pm 6.9\%$  with 95% confidence when the point estimate is 50%. Additional accuracy estimates are provided in the Table below.

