**Table 4: Accuracy Estimates with a Sample Size of 200 Subjects**

Estimated Proportion of Responders	Accuracy Estimate
5%	3.0%
10%	4.2%
15%	4.9%
20%	5.5%
25%	6.0%
30%	6.4%
35%	6.6%
40%	6.8%
45%	6.9%
50%	6.9%

**Note: Proportion of responders can be estimated with +/- accuracy with 95% confidence. The size of the 95% Confidence Interval would be 2×Accuracy**

Due to the recent enrollment plan change (enroll 50 patients or as the number of enrollment by 31-Dec-2016), Updated accuracy estimates with a sample size of 50 subjects, about the proportion of subjects with a highly or completely satisfied response after 16 weeks of ADA + MTX therapy based on an Investigator assessment and subject self-assessment, are provided in the table below.

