**Table 5: Accuracy Estimates with a Sample Size of 50 Subjects**

Estimated Proportion of Responders	Accuracy Estimate
5%	6.0%
10%	8.3%
15%	9.9%
20%	11.1%
25%	12.0%
30%	12.7%
35%	13.2%
40%	13.6%
45%	13.8%
50%	13.9%

**Note:** Proportion of responders can be estimated with +/- accuracy with 95% confidence. The size of the 95% Confidence Interval would be  $2 \times \text{Accuracy}$

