4.3 Sample Size

This study was planned to have a 30 month recruitment period where it was anticipated that approximately 200 subjects will be recruited. With this sample size the proportion of responders, defined as the proportion of subjects with a highly or completely satisfied response after 16 weeks of ADA/MTX therapy, based on an investigator assessment and subject self-assessment, can be estimated within $\pm 4.9\%$ with 95% confidence when the point estimate is 15%, within $\pm 6.4\%$ with 95% confidence when the point estimate is 30%, or within $\pm 6.9\%$ with 95% confidence when the point estimate is 50%. Additional accuracy estimates are provided in the table below.

Table 1. Accuracy Estimates with a Sample Size of 200 Subjects

Estimated Proportion of Responders (%)	Accuracy Estimate (%)
5	3.0
10	4.2
15	4.9
20	5.5
25	6.0
30	6.4
35	6.6
40	6.8
45	6.9
50	6.9

Note: Proportion of responders can be estimated with \pm accuracy with 95% confidence. The size of the 95% Confidence Interval would be $2 \times$ Accuracy.

Due to the enrollment plan change (enroll 50 patients or as the number of enrollment by 31 December 2016), updated accuracy estimates with a sample size of 50 subjects, about the proportion of subjects with a highly or completely satisfied response after 16 weeks of ADA/MTX therapy based on an investigator assessment and subject self-assessment, are provided in the table below.

Table 2. Accuracy Estimates with a Sample Size of 50 Subjects

Estimated Proportion of Responders (%)	Accuracy Estimate (%)
5	6.0
10	8.3
15	9.9
20	11.1
25	12.0
30	12.7
35	13.2
40	13.6
45	13.8
50	13.9

Note: Proportion of responders can be estimated with \pm accuracy with 95% confidence. The size of the 95% Confidence Interval would be $2 \times$ Accuracy.

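### The synopsis credits about 50 subjects with the precision of 200: ±4.9%, ±6.4% and ±6.9%, where 50 subjects give ±9.9%, ±12.7% and ±13.9%

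*Protocol*

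**What the plan says.** The synopsis has two consecutive sample-size paragraphs.

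- The first gives the expected recruitment and then the precision: "it is anticipated that approximately 50 subjects will be recruited. With this sample size the proportion of responders", followed by ±4.9%, ±6.4% and ±6.9% at proportions of 15%, 30% and 50%, with 95% confidence.
- The second refers to the change in the enrolment plan and says: "With 50 subjects the same proportion of responders can be estimated within" ±9.9%, ±12.7% and ±13.9% at the same three proportions and the same confidence level.

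Protocol Section 8.2 pairs the figures differently from the first of these paragraphs. It says "This study should have a 30 month recruitment period where it is anticipated that approximately 200 subjects will be recruited" and attaches ±4.9/6.4/6.9% to that number, with Table 4 headed "Accuracy Estimates with a Sample Size of 200 Subjects". It then reports the change to 50 and gives ±9.9/12.7/13.9% in Table 5, headed "Accuracy Estimates with a Sample Size of 50 Subjects". SAP Section 4.3 makes the same pairing in its Tables 1 and 2.

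**The concern.** In the first synopsis paragraph, the reference back to the sample size can only mean the 50 subjects just named. The same 50 subjects, endpoints and confidence level are thus given two precisions that cannot both be right.

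The study has one arm and states no hypothesis test or power calculation for its two primary endpoints, so the expected width of the confidence interval is the only quantitative sample-size statement it offers for them. A reader who takes the first paragraph at its word would expect, at an observed response of 30%, an interval of roughly 24% to 36% (30 ± 6.4). With 50 subjects the interval is roughly 17% to 43% (30 ± 12.7).

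This is operative synopsis text, not the amendment log. The summary of changes says that the synopsis was revised to agree with Amendment 2.

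**Working it through.** **Inputs**

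- Sample sizes: 50 (both synopsis paragraphs, Protocol Table 5, SAP Table 2) and 200 (Protocol Section 8.2 and Table 4, SAP Table 1).
- Proportions: 15%, 30% and 50%.
- Confidence: 95%, two-sided, z = 1.96. The notes under the tables define accuracy as half the width of the interval.
- Method: normal approximation, named in SAP Section 10.1.

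**Formula**

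Half-width = 1.96 × √(p(1 − p)/n)

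**Step 1. Reproduce the tables.** At n = 200 the formula gives all ten rows of Protocol Table 4 after rounding, and at n = 50 all ten rows of Table 5. The three rows used in the synopsis are:

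| p | n = 200 | Table 4 | n = 50 | Table 5 | First synopsis paragraph |
|---|---|---|---|---|---|
| 15% | 1.96 × √(0.1275/200) = 4.95% (4.949) | 4.9% | 1.96 × √(0.1275/50) = 9.90% | 9.9% | 4.9% |
| 30% | 1.96 × √(0.21/200) = 6.35% (6.351) | 6.4% | 1.96 × √(0.21/50) = 12.70% | 12.7% | 6.4% |
| 50% | 1.96 × √(0.25/200) = 6.93% | 6.9% | 1.96 × √(0.25/50) = 13.86% | 13.9% | 6.9% |

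**Step 2. Solve for the sample size behind ±4.9/6.4/6.9%.** From n = 1.96² × p(1 − p)/h², the implied n is 204, 197 and 202. Allowing for rounding of h to one decimal, the ranges are 199.9–208.2, 193.9–200.1 and 198.8–204.7. The only whole number in all three is 200. The same calculation on 9.9/12.7/13.9% gives 50 each time.

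**Step 3. Look for another method that would rescue the figures at n = 50.**

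| Method at n = 50 | 15% | 30% | 50% |
|---|---|---|---|
| One-sided 95% | 8.3% | 10.7% | 11.6% |
| Wilson | 9.9% | 12.3% | 13.4% |
| Continuity-corrected | 10.9% | 13.7% | 14.9% |
| Exact (half the interval width) | 10.5% to 11.0% (7 or 8 of 50) | 13.4% | 14.5% |

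None comes near 4.9/6.4/6.9%.

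**Step 4. Size of the discrepancy.** Theory gives √(200/50) = 2. The printed figures give 9.9/4.9 = 2.02, 12.7/6.4 = 1.98 and 13.9/6.9 = 2.01.

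Put another way, the standard errors at n = 50 are 5.05%, 6.48% and 7.07%. The stated half-widths are therefore 0.970, 0.988 and 0.976 standard errors, and intervals of that width carry 66.8%, 67.7% and 67.1% confidence, not 95%.

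**The case against.** The strongest reply is that this is editorial. The correct figures come in the very next paragraph and again in Protocol Table 5 and SAP Table 2. Protocol Section 8.2 and SAP Section 4.3 pair every figure with the right sample size. No test, stopping rule or decision uses the stated precision, and the reported intervals will be computed from the data. The half-widths themselves are calculated correctly; what is wrong is the sample size they are attached to.

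Most of that is fair, and it limits the consequence. It does not remove the error: the synopsis still claims for both primary endpoints a precision that the design does not have. The 67% figure is only another expression of the factor of two, since no interval of ±4.9/6.4/6.9% will be reported.

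A practical point also stands. The subject number and the precision are in two linked sentences, so labelling the precision sentence as the 200-subject plan works only if its reference back to 50 is reworded too.

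The remaining differences are matters of wording. Section 8.2 keeps the 200-subject plan in the present tense, whereas the SAP writes "This study was planned to have a 30 month recruitment period where it was anticipated that approximately 200 subjects will be recruited". Only the synopsis attaches a recruitment period to 50 subjects: "This study will have a 12 month recruitment period where it is anticipated that approximately 50 subjects will be recruited". Section 8.2 and the SAP do give the 31 December 2016 enrolment limit, and nothing else in the documents confirms the 12 months.

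**Conclusion.** The concern holds. The first synopsis paragraph assigns the 200-subject half-widths to about 50 subjects and so understates the uncertainty of both primary proportions by a factor of about two. The error is confined to that paragraph.

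It changes neither the sample size nor the analysis. The reduction from 200 to 50 followed from low recruitment, with enrolment also limited by the 31 December 2016 date; precision only describes what 50 subjects deliver.

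The conclusion rests on the interval method named in the SAP and on all 50 subjects counting in the denominator, which non-responder imputation provides for everyone in the ITT population. If enrolment closes at the date limit with fewer than 50, the half-widths will be wider than ±9.9/12.7/13.9%. The partial update is an inference about how the error arose; the finding does not depend on it.

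**What to change.** In the synopsis, do one of the following:

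- Delete the sentence giving ±4.9%, ±6.4% and ±6.9%. This is the simpler course.
- Keep it as history, stating that it describes the original plan of about 200 subjects, and reword the link so that it no longer refers to 50.

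Either way, leave ±9.9%, ±12.7% and ±13.9% as the only precision given for 50 subjects.

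As a secondary wording change, put the 200-subject, 30-month text of Protocol Section 8.2 in the past tense, as SAP Section 4.3 does, and state there the recruitment period that applies to the 50-subject plan once the sponsor has confirmed it.

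The cost is a text correction: no extra patients and no change to the sample size or the analysis. The precision shown in the synopsis becomes less favourable.
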